4.9 Trial Termination

Study participation is voluntary, and participants may withdraw at any time. The DSMB will report to the ethics committees and investigators if stopping the study is required.

In general, once a participant is randomised, he/she will remain in the study unless the investigator believes it is not safe for the participant to continue. However, the criteria below will be used to determine whether use of the AHCL should be discontinued for a participant.

1. Severe hypoglycaemia (seizure or coma or any episodes requiring glucagon).
2. Severe diabetic ketoacidosis (venous ph <7.2)
3. Non-compliance with the protocol or development of a new medical condition or need for chronic use of a medication which in the judgment of the investigator increases risk for the participant

If AHCL use is stopped according to the above criteria, but the participant is willing, they will remain in the study and will continue to make all of the scheduled visits and participate in all monitoring.

The primary analysis will be intention to treat. Since participants in the usual care arm are following their normal diabetes care regimen, there will be no change in their participation in the study if they experience one of the events that would trigger stopping.

Criteria for Suspending/Stopping Overall Study

The DSMB will provide guidance to the Lead Investigator as to whether the overall study should be stopped.

In case of a recurring system malfunction or participant safety issue observed with multiple participants, the overall study will be suspended while the problem is diagnosed. The study may resume if the underlying problem can be corrected by a protocol or system modification that will not invalidate the results obtained prior to suspension.

The primary safety outcome will be

Severe hypoglycaemia (coma, convulsion or any episodes requiring glucagon). A sequential monitoring approach described by Kramar and Bascoul-Mollevi (2009) will be taken to determine study cessation rules due to excess severe hypoglycaemia. As hypoglycaemia events are experienced during the study, the DSMB will be notified in real time. The maximum acceptable rate of severe hypoglycaemia as well as the approach taken with regard to 'alpha spend' to preserve the nominal alpha of 0.05 will be determined in conjunction with the DSMB prior to the commencement of the study.

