6.2 Permitted medications/treatments

For severe hypoglycaemia, intramuscular glucagon can be administered.

For ketosis > 0.6 mmol/l with blood glucose > 15mmol/l, insulin (rapid-acting) is administered with an insulin pen.

This is taught to every family at the time of diagnosis of T1D and review of their knowledge is established in subsequent clinic follow-ups.

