8.2 Safety

This is a cohort of young children with T1D supervised by their parents/caregivers.

Participants will be contacted on a weekly basis (or more frequently as required) during the entire duration of the feasibility phase and for at least 4 weeks of the larger RCT after commencement of AHCL to review progress. During the feasibility phase, the research nurse will also follow the participant in real-time. Real-time glucose levels will also be available to the caregiver/parent at all times.

- a. Participants with high blood/sensor glucose levels will be advised to test for blood ketones.
- b. Participants with hypoglycaemia will be advised to take appropriate clinical action.
- c. Weekly review of time spent in hypoglycaemia range will be evaluated by the research doctor. Any instance of a week where percentage of time spent <3.9 mmol/l exceeds 8% and/or percentage of time <3 mmol/L exceeds 2 % will be recorded as an adverse event.
- d. Participants using the AHCL system will be informed to contact the research diabetes educator if they experience technical issues with the sensor and/or system and to revert to manual mode (standard pump) in the interim.
- e. Participants in the control group will be advised to follow the clinical pathway while participants in the intervention group will be advised to contact the research doctor/diabetes educator.
- f. In the event of device (pump) failure, the participant will be advised to switch to their standard pump therapy (own pump) and contact the research doctor/diabetes educator.
- g. Patients are educated regarding awareness of insulin infusion failure (rising blood glucose levels and ketones) and how to manage this (using standard injected subcutaneous insulin, and change insulin infusion set).
- h. Any admissions to hospital for DKA or severe hypoglycaemia will be reported to the principal investigator within 24hrs with notification to the lead site.
- i. Establishment of Data and Safety Monitoring Board (DSMB) to review progress

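### The 24-hour report in section 8.2(h) is triggered by hospital admission, but the primary safety event in 4.9 and 8.4 needs no admission, and no stated step carries non-admitted events to the DSMB

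*Protocol*

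**What the plan says.** **Definition.** Section 4.9 gives the primary safety outcome as "Severe hypoglycaemia (coma, convulsion or any episodes requiring glucagon" and applies a sequential monitoring rule to it. The same section makes nearly the same event the first criterion for discontinuing AHCL: "Severe hypoglycaemia (seizure or coma or any episodes requiring glucagon". Section 8.4 repeats the definition under severe adverse events and lists inpatient hospitalisation as a separate item.

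**Notification promised.** Section 4.9 continues: "As hypoglycaemia events are experienced during the study, the DSMB will be notified in real time".

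**Deadline set.** Section 8.2(h) reads "Any admissions to hospital for DKA or severe hypoglycaemia will be reported to the principal investigator within 24hrs". The lead site is to be told as well. Section 8.4 gives definitions but no deadline, sender or recipient.

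**Treatment outside hospital.** Section 6.2 states: "For severe hypoglycaemia, intramuscular glucagon can be administered". It adds that families are taught this at diagnosis.

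**Contact with the study.** Section 8.2(e) differs by arm. In the AHCL arm, "participants in the intervention group will be advised to contact the research doctor/diabetes educator". The instruction for the other arm is not the same: "Participants in the control group will be advised to follow the clinical pathway". Section 8.1 also lists contacting the research team, without a time limit. Section 8.2 sets weekly contact "for at least 4 weeks of the larger RCT after commencement of AHCL to review progress".

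**The concern.** The protocol counts one set of events and puts a deadline on a narrower set. A convulsion at home, or a low treated with glucagon by a parent and resolved without admission, is a primary safety event, meets AHCL discontinuation criterion 1 and is a severe adverse event under 8.4. On the natural reading it does not start the 24-hour clock in 8.2(h).

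A sequential boundary can act only on events that have reached the board. The DSMB cannot be told in real time of something the study team has not yet learned. The discontinuation criterion likewise needs someone on the study to know that it has been met. The participants are young children, 70 are planned for the RCT, and the device is described as investigational, so each severe event carries weight. If the routes to the study team also differ by arm, the between-arm comparison of the main safety outcome is exposed to unequal capture.

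**Working it through.** No arithmetic decides this point, and the protocol has no figure to reproduce. Section 4.9 leaves the maximum acceptable rate and the alpha spending to be settled with the DSMB, so the boundary cannot be computed. The check is a comparison of the passages.

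**1. Can a qualifying event occur without admission?** Yes. Sections 4.9 and 8.4 count any glucagon-treated episode, 6.2 permits glucagon and says families are taught its use, and 8.4 lists severe hypoglycaemia and hospitalisation as separate items.

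**2. Does 8.2(h) cover such an event?** Not on its natural reading, in which admission governs both DKA and severe hypoglycaemia. A second reading, admissions for DKA on the one hand and severe hypoglycaemia on the other, would cover it but is strained.

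**3. Does another provision carry the event to the study team within a stated time?**

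| Provision | Who | What it gives | What is missing |
|---|---|---|---|
| 4.9, real-time DSMB notice | All hypoglycaemia events, admitted or not | The outcome promised | The step from family or site to DSMB |
| 8.1, contact with research team | Not limited by arm | An instruction to make contact | Time limit, onward report |
| 8.2(e) | AHCL: research team; control: clinical pathway | A contact route | Time limit, event type; no research-team route for controls |
| 8.2, weekly contact | RCT: at least 4 weeks after AHCL start | A regular opportunity to ask | A fixed schedule after that |
| 8.2(c), weekly review | No arm or end date stated | Percentage of time in low ranges | Any question about seizures or glucagon |
| 4.2, data review at 8 weeks | AHCL | Review of CGM data | Any listed event question |

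On 8.2(c): a week has 7 × 24 = 168 hours. The recording thresholds of 8% below 3.9 mmol/L and 2% below 3.0 mmol/L equal 0.08 × 168 = 13.4 hours and 0.02 × 168 = 3.4 hours. A short severe episode need not reach either.

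**4. Would the scheduled visits recover the event later?** For severe hypoglycaemia, section 4.2 lists:

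- Visit 3, before randomisation: events in the run-in.
- Visit 5, controls only, 11 weeks after randomisation: sensor insertion, meter testing instructions and uploads, with no event item.
- Visit 6: events since Visit 5 in controls and since Visit 4D in the AHCL arm.

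For controls, the interval from randomisation to Visit 5 therefore falls under no listed visit item. In the AHCL arm the Visit 6 look-back begins at Visit 4D. Before that, weekly contact covers the first 4 weeks of AHCL use, although the RCT visit list does not name severe hypoglycaemia among the items to be asked. After Visit 4D, the listed study contacts are the 8-week data review and Visit 6.

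**The case against.** The strongest reply is that 4.9 already requires real-time DSMB notice of hypoglycaemia events and does not limit it to admissions. Section 8.2(h) adds a deadline for one class of event and does not say that other events go unreported. AHCL families, the only ones to whom the discontinuation rule applies, are told to contact the research team, so detection need not wait for a visit. Weekly contact is for at least 4 weeks and may be more frequent. The working route may sit in DSMB arrangements or in the manual of operations, neither of which is shown.

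Most of this stands. A reader might infer that home-treated events will not be reported in time, so that the boundary is crossed late or a child stays on AHCL after meeting a criterion. The documents do not support that: they promise the notice and leave open how the event arrives. Nor do they support a stated maximum delay in either arm. The 8-week review is of CGM data, Visit 5 has no event item, and unscheduled contact is possible throughout.

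Two further limits apply. Section 8.2(e) names no event type and sits among items on device problems, so treating it as the route for severe hypoglycaemia is interpretation. Section 4.9 does not say whether control events enter the boundary, so an effect of missing control events on the stopping rule is not shown.

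The reply does not remove the mismatch. The protocol does fix a deadline, its trigger is narrower than its own safety outcome, and no step connects the remaining events to the promise in 4.9.

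**Conclusion.** The point holds as an internal mismatch: 8.2(h) is narrower than 4.9 and 8.4, and no stated step or time limit ensures that a non-admitted severe event reaches the study team in time for real-time DSMB notice. The exposure is greatest in the RCT after the first 4 weeks of AHCL, when no regular contact is fixed, and in controls, for whom no listed visit item covers randomisation to week 11. In controls an event could therefore be missed altogether, which affects the between-arm safety comparison whether or not control events enter the boundary.

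No numerical size can be given. The protocol does not state how many severe events are managed without admission, and the conclusion does not depend on that share. It rests on two assumptions: that 8.2(h) is read naturally, with admission governing both conditions, and that no document outside the protocol sets a wider trigger. If one does, 8.2(h) still needs to agree with it. The point concerns reporting only and implies nothing about treatment.

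**What to change.** Reconcile 8.2(h) with 4.9 and 8.4:

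- Trigger the 24-hour report on any event meeting the protocol's own definition of severe hypoglycaemia or severe DKA, in either arm, whether or not the child is admitted. Keep the existing report of admissions, since it also covers DKA that is not severe by the 8.4 definition.
- Cite 4.9 and 8.4 by number in the trigger, because 8.1 and the Visit 1 history item describe severe hypoglycaemia by third-party assistance instead.
- State that the lead site forwards each report to the DSMB, so that the real-time promise in 4.9 has a named route.
- Ask families in both arms to notify the research team of any such event, for example by a line in the participant record book.
- Start the Visit 6 look-back for severe hypoglycaemia at randomisation in both arms. DKA and hospital admissions share the same look-back and should move with it.

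The cost is a short amendment and a few more expedited reports. No new visits are needed, and no treatment or discontinuation rule changes.

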8.3 Data and Safety Monitoring Board

To safeguard the interests of the study participants, monitor the main safety outcome measures, and monitor the overall conduct of the study, DSMB will be established. The board will receive and review information on the progress and accruing data and provide advice on the conduct of the study to the Investigators.

8.4 Adverse event reporting

Adverse Event

Any undesirable clinical occurrence in a participant whether it is considered to be device related or not, that includes a clinical sign, symptom or condition and/or an observation of an unintended technical performance or performance outcome of the device.

Adverse Device Event

A clinical sign, symptom or condition causally related to the device implantation procedure, the presence of the device, or the performance of the device system.

Severe adverse events

1. Severe hypoglycaemia (seizure or coma or any episodes requiring glucagon)
2. Severe Diabetic ketoacidosis (venous pH <7.2)
3. Requiring inpatient hospitalisation
4. A life-threatening event

8.5 Follow-up of Adverse Events

The follow-up of participants after adverse events will follow standard clinical care pathway of the institution.

9 Data Management, Statistical Analysis and Record Keeping

9.1 Statistics and Interim Analysis

Feasibility Phase

No statistical tests will be conducted with the difficulties encountered/solutions identified at the weekly meetings of the study team. Rather, all difficulties encountered will be discussed on a weekly basis and be collated into a single table at the end of the feasibility phase. This information will be used to design the manual of operations for the larger RCT.

Recruitment rate will be presented as a rate of recruitment per week and retention rate will be presented as a proportion of recruited participants that continued to wear the device to the end of the feasibility phase.

The mean, standard deviation, median, and interquartile range will be presented for insulin to carbohydrate ratio, insulin active time, and percent time in various glycaemic ranges at the end of the phase.

No interim analyses are planned apart from the DSMB safety review reported above.

RCT Phase

Data collected at baseline and Visit 6 will be used to assess the effectiveness of AHCL therapy as compared to standard therapy.

To test for an effect of treatment group on the primary outcome, an ANCOVA including treatment, baseline percent time in range adjusting for minimisation factors will be conducted on an intention to treat basis. Multiple imputations will be used to handle missing data: a multivariate normal imputation approach will be taken. Results will be presented as the mean difference in the percent time in target range at the end of the study between treatment arms with 95% confidence interval and p value.

Model residuals will be used to assess model fit. If the residuals indicate poor model fit, the outcome variable will be transformed and the model refitted and evaluated. If poor model fit cannot be addressed, nonparametric analysis will be performed.

In the event that residuals are not normally distributed: the Mann–Whitney–Wilcoxon (Wilcoxon Rank-Sum) Test will be employed if raw data are symmetric; if raw data are non-symmetric, bootstrap methods will be used to test the difference between groups.

Continuous secondary outcomes (glycaemic, auxological, clinical, psychosocial) will be analysed using the ANCOVA approach described above. The same assessment of model residuals will be conducted, and the appropriate analysis approach utilised. Where parametric methods are employed using the untransformed outcome measure, mean difference with 95% CI will be presented; where data are transformed, the retransformed effect with 95% confidence intervals will be presented as an indication of the relative effect of the intervention; where non-parametric methods are employed, Hodges-Lehmann median difference with robust 95% CI will be presented.

Secondary count outcomes will be analysed using Poisson regression or, where overdispersion is apparent, negative binomial model with a maximum likelihood-estimated dispersion parameter. 'Exposure' will be the number of hours wearing the sensor for CGM-derived outcomes and total number of days enrolled in the study for non-CGM-derived outcomes.

To assess the cost effectiveness of the intervention, the 'cost per quality of life year (QALY)' will be calculated using an incremental cost effectiveness ratio.

All hypothesis testing will be two-sided with an α of 0.05. No corrections for multiplicity are planned to control Type I error; rather, the effectiveness of the intervention will be assessed based on the clearly specified primary outcome; secondary outcomes are exploratory in nature and will be labelled as such in publications arising from the study.

No interim analyses are planned apart from the DSMB safety review reported above.

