Visit 4D: Review of AHCL (after 4 weeks from commencement of AHCL, 1 hour)

Face-to-face meeting to upload insulin pump, review CareLink reports and revise settings (CHO ratio and Insulin action time)

Participants will be issued with enough consumables for the study.

Research staff will review CGM data at 8 weeks' with participants encouraged to contact the team if support/assistance required.

VISIT 5 (11 weeks after randomisation for control arm only)

Visit 5A: Insertion of blinded CGM: This constitutes first of the two sensors, each sensor provides data for 7 days. Parents will be instructed to test their children for a minimum 3 to 4x/day using the study meter.

Visit 5B: Insertion of 2nd blinded CGM: Participants will return 7 days after sensor insertion to remove and download the first week of CGM data. The study meter will be uploaded. A new sensor will be inserted and a fresh transmitter attached.

A total of 2 weeks of blinded sensor is required with at least 10 days of data. In participants who do not meet this requirement, repeat sensors will be offered till a maximum of 4 attempts of data collection

Visit 5C: Insertion of 3rd blinded sensor (if applicable)

Visit 5D Insertion of 4th blinded sensor (if applicable)

VISIT 6 (1 week after last blinded sensor) **End of RCT Phase**

The following data will be collected:

1. Auxological
 - a. Height
 - b. Weight
 - c. BMI
2. Diabetes clinical
 - a. HbA1c
 - b. Total daily dose of insulin (mean of previous 7 days)
 - c. Pump upload (for intervention group)
 - d. Severe hypoglycaemia since Visit 5 for Control arm / Visit 4d for Intervention arm
 - e. Diabetic ketoacidosis since Visit 5 for Control arm / Visit 4d for Intervention arm
 - f. Hospital admissions since Visit 5 for Control arm / Visit 4d for Intervention arm
3. Psychology measures: Psychological scales will be administered to parents on an electronic platform.
 - a. Functional health status: Quality of life (QOL) WHO 5, EQ5D
 - b. Fear of hypoglycaemia: Hypoglycaemia fear survey Parent
 - c. Diabetes-related distress: Problem Areas in Diabetes PAID-Parent version
 - d. Anxiety: GAD-7
 - e. Sleep quality: Pittsburgh Sleep Quality Index
 - f. Technology acceptance and satisfaction: DTQ
4. 24-hour food recall interview (to capture dietary pattern)
5. Parents of participants will be offered a semi-structured interview at the end of the study to share the lived experiences with use of new technology.

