5.4 Participant withdrawal criteria

(a) when and how to withdraw participants from the investigational product/study treatment;
The participant may withdraw from the study at any time. They can do so by contacting the research staff.

(b) the type and timing of the data to be collected for withdrawn participant(s);
As this is an intention-to-treat, the data for withdrawn participants will be used for analysis

(c) whether and how participants are to be replaced;
Participants will not be replaced.

(d) the follow-up for participants withdrawn from the investigational product/study treatment.
The participants will go back on their standard therapy and will be followed up as their regular clinic visits.

6 Treatment of Participants

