9.6 Data management

Data collected from each site will be stored in the respective study sites' secured servers, in accordance to data storage policies in each site. These data will all be entered, in a de-identified manner into a robust

data capture platform, REDCap, in which the forms were built and validated by a data manager based in Telethon Kids Institute.

All anonymised data will not be able to be linked back to any individual participant. Data will be stored on secure servers and electronic device capture systems with secure access for study staff only. All data will be stored at least for 25 years in line with GCP requirements on secure servers. Hard copies of participant notes will be stored in secure filing cabinets at each site and archived in secure facilities' at the end of the study.

All anonymised data will be risk rated at the completion of the study and stored in data repositories according to the Institution's data sharing policies and plan, and may be used for unspecified future research. Only published and permanently de-identified data will be deposited into publicly accessible repositories which will be safeguarded by Australian Data Archives (ADA) through a data sharing agreement with Telethon Kids Institute. The ADA main server is based in ANU and is a Core Trust Seal Certified repository.

Medtronic CareLink® System:

This system allows the study device to send information over the internet using a telecommunication network (such as a cellular network, wireless network, etc.). The information available from the Medtronic CareLink system is the same information the study team would collect from your device during an in-person office visit. Medtronic will receive participant's coded (deidentified) device data from CareLink®.

Medtronic takes steps to protect the privacy of the health information sent to the Medtronic CareLink Network over the internet. However, Medtronic cannot guarantee the health information is protected against unauthorised interception.

9.7 Procedures for missing, unused and spurious data:

Multiple imputations using multivariate normal regression imputation will be employed to account for missing/spurious data. Analysis using complete case and multiple imputation methods will be presented.

10 Monitoring / Audit

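### An AHCL child who no longer wears the study sensor has no scheduled primary outcome, so imputation under missing at random can overstate the intention-to-treat effect

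*Protocol*

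**What the plan says.** **Analysis.** Section 4.9 states "The primary analysis will be intention to treat"; Sections 7.2 and 9.1 repeat this, and Section 5.4(b) says that withdrawn participants' data are used. For missing values Section 9.1 says "Multiple imputations will be used to handle missing data: a multivariate normal imputation approach will be taken", without naming the variables in the imputation model. Section 9.7 adds "Analysis using complete case and multiple imputation methods will be presented".

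**Outcome collection.** Section 7.1 defines the primary outcome as time in range from two weeks of blinded CGM, with no restriction to one arm. A child with fewer than 10 days at 70% valid readings counts as missing. Section 4.2, however, heads the end-of-study sensor visits "VISIT 5 (11 weeks after randomisation for control arm only)", and the note under Figure 2 says the same. For the intervention group, Visit 6 lists a pump upload.

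**Leaving the device.** Section 4.9 says "If AHCL use is stopped according to the above criteria, but the participant is willing, they will remain in the study", with all scheduled visits and monitoring. Under Section 8.2(f), on pump failure, "the participant will be advised to switch to their standard pump therapy (own pump)". Of those who withdraw, Section 5.4(d) says "The participants will go back on their standard therapy and will be followed up as their regular clinic visits".

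**The concern.** The pump upload is the only scheduled end-of-study source of sensor data in the AHCL arm. It yields time in range only for a child still wearing the study sensor. A child who is not wearing it has no outcome measurement to attend: the promise in Section 4.9 that stoppers "they will remain in the study and will continue to make all of the scheduled visits" does not help, because for this arm those visits include no outcome sensor.

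Multivariate normal imputation, as normally run, assumes missing at random. With arm in the model and nothing observed off device, the imputed values come from AHCL children whose data were captured, who are mostly on the device. A child back on standard therapy would be given on-treatment results. The complete-case analysis promised beside it estimates the same quantity, so the two would agree without revealing the problem.

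The mechanism is one-sided. Controls wear an outcome sensor that does not depend on their therapy, and a control who drops out was on standard therapy in any case. At stake is whether the primary estimate answers the intention-to-treat question or one closer to the effect had all children stayed on AHCL.

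**Working it through.** **Inputs from Section 9.2:** difference 8 points, SD 11.5, two-sided alpha 0.05, 80% power, 31 per group, total dropout up to 10%, 70 recruited (35 per arm). **Assumptions not in the protocol:** the 8 points apply on device; a child off device returns to the control mean; the split of dropout between arms; and, for the simulation, a baseline-outcome correlation of 0.5.

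**The plan's own figure.** n per group = 2 × (1.960 + 0.842)² × 11.5² / 8² = 32.4, so 33 against the stated 31; power at 31 is 78.2%. This is close enough to take the inputs as they stand. For dropout, 62 / 0.9 = 68.9, so 69, consistent with 70.

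**Size of the overstatement.** Let f be the share of the AHCL arm with a missing outcome, m the share of those who are off device, and Δ the on-device effect. The intention-to-treat effect is Δ(1 − f·m). Imputation within arm under missing at random gives about Δ. The overstatement is f·m·Δ.

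- f = 0.10, m = 1: 8 × 0.90 = 7.2 against 8.0; overstated by 0.8 (0.8/7.2 = 11%).
- f = 0.10, m = 0.5: 8 × 0.95 = 7.6; overstated by 0.4.
- f = 0.10, m = 0: no overstatement.
- All 0.10 × 70 = 7 dropouts in the AHCL arm, f = 7/35 = 0.20, m = 1: 8 × 0.80 = 6.4; overstated by 1.6 (1.6/6.4 = 25%).
- Δ = 0: f·m·0 = 0 for every f and m, so this mechanism adds no false positives.

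**Simulation check** (3,000 trials per row, 35 per arm, ANCOVA on baseline, mean estimates in points):

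| Missing AHCL / control | AHCL off device | All outcomes observed | MI with arm | Complete case | MI without arm | Control-based MI for all missing |
|---|---|---|---|---|---|---|
| 4 / 3 | 4 | 7.1 | 8.0 | 8.0 | 7.2 | 7.1 |
| 4 / 3 | 2 | 7.6 | 8.0 | 8.0 | 7.2 | 7.1 |
| 4 / 3 | 0 | 7.9 | 7.9 | 7.9 | 7.1 | 7.0 |
| 7 / 0 | 7 | 6.4 | 8.0 | 8.0 | 7.1 | 6.4 |
| 7 / 0 | 3 | 7.3 | 8.0 | 8.0 | 7.1 | 6.4 |

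Three things follow. Imputation with arm and complete case share the same bias. Leaving arm out does not repair it reliably: the result is close to the truth in the first row, too high in the fourth and too low in the others. Control-based imputation recovers the target when all missing AHCL children are off device, but undershoots when it is also applied to children still on AHCL.

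**Consequence for power.** With 35 per arm and no baseline adjustment, power = Φ(δ / (11.5√(2/35)) − 1.96). This gives 82.9% at 8.0, 74.5% at 7.2 and 64.4% at 6.4. These are powers for different true effects when AHCL works, not false-positive rates.

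**The case against.** A reader might infer that the imputation sentence is itself an error and that the primary effect will certainly be overstated. The protocol does not support that, for four reasons.

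- The imputation variables are not given. They are commonly left to the statistical analysis plan, which is not at hand, and the sign and size of any bias depend on them.
- Stopping AHCL is not the same as losing the sensor. The Study Device Overview describes a Manual Mode that still uses sensor glucose. Section 8.2(d) sends children with technical problems to that mode in the interim, and Section 4.9 keeps willing stoppers in all monitoring. Such a child can supply an observed off-treatment outcome, as intention to treat requires. Section 8.2(f) does not say that the return to the own pump is permanent.
- Missing does not have to mean off treatment. Under Section 7.1 a child still on AHCL with too few valid sensor days is also missing; if all the missing are of this kind, the bias is zero.
- The larger figure needs every planned dropout to be an off-device AHCL child with no remaining benefit.

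All four stand, and they limit the claim. They do not remove its core. For a child who is off the study sensor, no observed value informs the imputation, so a better specified model cannot recover what was not collected. That follows from the visit schedule, which the protocol itself fixes.

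**Conclusion.** The point holds in conditional form. Section 4.2 schedules end-of-study blinded CGM for controls only, against the unrestricted definition in Section 7.1. AHCL children who have left the study sensor are therefore left without a primary outcome in a trial that promises intention to treat. The effect is overstated when missing AHCL children are mainly off device and are imputed with arm in the model, or are dropped. The amount is 0 to about 0.8 points with 10% of the AHCL arm missing, and about 1.6 of 8 points in the extreme case. These figures assume an 8-point effect on device and none off it; any residual benefit would shrink them.

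A reader might also infer a raised type I error, or that control-based imputation should become the primary method. Neither follows. The bias is proportional to the true effect and vanishes when there is none. Control-based imputation replaces one untestable assumption with another, and it understates the effect if applied to children still on AHCL. The change is worth making because it is cheap and lets the trial deliver the estimate it promises.

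**What to change.** 1. **Section 4.2 (Visit 5 and the Figure 2 note).** Offer the existing Visit 5 blinded sensors to every randomised AHCL child not wearing the study sensor at week 11, and include those readings in the intention-to-treat analysis. Reconcile this with Section 7.1, which names blinded CGM for both arms and starts it at 13 to 15 weeks.
2. **Sections 9.1 and 9.7.** Keep multivariate normal imputation as the primary approach. Add a control-based (reference-based) sensitivity analysis limited to AHCL children known to be off the device whose outcome is still missing. Children still on AHCL whose sensor data fell short keep the standard imputation.

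The cost is up to two sensor visits for a few children, more if repeat sensors are needed, plus one extra analysis. The estimate may come out slightly smaller.
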